7.2 CLINICAL LABORATORY MEASUREMENTS

Blood will be obtained at the time points described in the Schedule of Activities. [Appendix 2](#) lists all of the specific tests that will be performed.

Investigators may have additional blood tests performed for the purpose of planning treatment administration, dose modification, or following adverse events.

7.2.1 PSA

Serum PSA will be measured using local laboratory during Screening, on C1D1, on D1 of every cycle thereafter during the 12 month treatment period, and every 28 days during follow up until the date of confirmed PSA progression by PCWG3 criteria.

7.3 EXPLORATORY BIOMARKERS (DISCONTINUED)

An optional biopsy and biomarker blood collection was to be conducted under the PROMOTE study (CC155518, IRB# 15-18365), as an optional enrollment option. The PROMOTE study has closed to accrual and will no longer be able to financially support the biopsy, biomarker collection, and downstream correlates. Therefore, we are discontinuing the biopsy and biomarker blood collection moving forward described in the italicized paragraph below (as of Amendment 8.0). Any specimens collected under prior protocol versions (i.e., prior to implementation of Amendment 8.0) may continue to be stored and/or used as permitted according to the PROMOTE study protocol and ICF.

Metastatic tumor biopsy tissue acquired at UCSF will undergo genomic characterization as described in UCSF protocol CC# 155518. In brief, freshly frozen tissue will undergo laser capture microdissection and exome/transcriptome sequencing. Formalin-fixed paraffin embedded tissue will undergo pathologic evaluation and targeting next-generation sequencing using CLIA-certified laboratory. Whole blood for exploratory analysis of circulating nucleic acids including analysis of circulating tumor DNA and long noncoding RNA (lncRNA) will be collected on C1D1, every 3 cycles during protocol treatment, at the end of study treatment, and at the time of PSA progression. Germline mutation testing to evaluate for alterations in BRCA2 and other DNA repair pathway genes will be performed at baseline if patients give optional consent for testing. Germline mutation testing is not performed in a CLIA environment and, therefore, will not be reported back to patients.

PSMA imaging characteristics including the number, distribution and avidity of metastatic lesions will be characterized by trained nuclear medicine physician.

8 STUDY ASSESSMENTS BY VISIT ([APPENDIX 1](#))

8.1 SCREENING (WITHIN 42 DAYS OF RANDOMIZATION, UNLESS OTHERWISE SPECIFIED)

- Review the study with the patient (patient's legal representative) and obtain written informed consent
- Collect archival primary prostate cancer tissue (optional)

- PSMA (prostate specific membrane antigen) PET scan. Imaging may use Ga-PSMA-11 or other PSMA PET tracer. Either PET/MR or PET/CT is allowed (within 12 weeks of randomization).
- Record demographics data
- Record medical history, including history of prostate cancer, diagnosis date, and prior treatments
- Record concomitant medications
- Perform a physical examination
- Perform and record vital signs and ECOG performance status grade
- Collect blood for clinical laboratory assessments including hematology tests, total bilirubin (and direct bilirubin if total bilirubin > 1.5 ULN), ALT, AST, alkaline phosphatase, BUN or creatinine, albumin, and LDH.
- Collect blood for PSA
- Collect blood for testosterone
- Collect blood for Thyroid Stimulating Hormone (TSH)
- Obtain DXA bone density scan (femoral neck and lumbar spine)
- If patient is confirmed eligible by the medical monitor, randomize patient and proceed to Cycle 1 Day 1 visit (randomization can occur on C1D1 or within 7 days prior to C1D1)

8.2 CYCLE 1 DAY 1

- Record changes to concomitant medications
- Record any adverse events
- Perform abbreviated physical examination
- Perform and record vital signs and ECOG performance status
- Collect blood for clinical laboratory assessments including hematology tests, total bilirubin (and direct bilirubin if total bilirubin > 1.5 ULN), ALT, AST, alkaline phosphatase, BUN or creatinine, and LDH. Screening evaluations can be used if done within 4 days of Cycle 1 Day 1.
- Collect blood for PSA
- Collect blood for TSH
- Dispense study drug

8.3 DAY 1 OF CYCLES 2-4, THEN DAY 1 OF EVERY 2 CYCLES STARTING FROM CYCLE 5 THROUGH C13 (C5, C7, C9, C11, C13) (+/- 7 days) UNLESS OTHERWISE SPECIFIED

- Record any adverse events
- Record changes to concomitant medications

- Dispense study drug
- Assess study drug compliance
- Perform abbreviated physical examination
- Perform and record vital signs and ECOG performance status
- Collect blood for clinical laboratory assessments (including hematology tests, total bilirubin (and direct bilirubin if total bilirubin > 1.5 ULN), ALT, AST, alkaline phosphatase, BUN or creatinine, and LDH.
- Collect blood for PSA measurement (Day 1 of every treatment cycle)
- Stereotactic body radiation therapy administered 60 days following initiation of apalutamide therapy
- Collect blood for thyroid stimulating hormone test every 4 cycles starting Cycle 5 Day 1 (C5D1, C9D1, C13D1).

8.4 END OF TREATMENT VISIT

- Record any adverse events
- Record changes to concomitant medications
- Assess study drug compliance
- Perform abbreviated physical examination
- Perform and record vital signs and ECOG performance status
- Collect blood for clinical laboratory assessments (including hematology tests, total bilirubin (and direct bilirubin if total bilirubin > 1.5 ULN), ALT, AST, alkaline phosphatase, BUN or creatinine, and LDH.
- Collect blood for PSA measurement
- Collect blood for TSH

8.5 SAFETY FOLLOW-UP (30 DAYS FOLLOWING THE LAST DOSE OF STUDY DRUG)

- Record any adverse events
- Record changes to concomitant medications

8.6 POST-TREATMENT PERIOD UNTIL CONFIRMED PSA PROGRESSION BY PCWG CRITERIA

- Collect blood for PSA measurement every 28 days (+/- 7 days) until confirmed PSA progression by PCWG3 criteria. In the event of disease progression per PCWG3 or initiation of a new non-protocol therapy, patients will be discontinued from the study, and further PSA tracking will no longer be required

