Duration of Therapy	
Patients will continue protocol treatment until the first occurrence of one of the following:
 
 • Disease progression by PCWG3 criteria • Unacceptable adverse event(s) related to apalutamide or SBRT • Completion of treatment (52 weeks for apalutamide) • Patients decides to withdraw from the study • Significant patient non-compliance with protocol • General or specific changes in the patients' condition render the patient unacceptable for further treatment in the judgment of the investigator.
Duration of Follow up	Patients will continue on study in follow up until disease progression by PCWG3 or withdrawal from study, whichever occurs first.
Duration of Study	The anticipated study duration is approximately 36 months.
Study Drugs/ Treatments	
 • Apalutamide will be administered orally on a continuous daily dosing regimen, at a starting dose of 240 mg once daily (4 x 60-mg tablets), until the completion of 12 months of treatment, unacceptable toxicity, or PSA progression, whichever occurs soonest. • SBRT will be delivered by treating radiation oncologist according to standard institutional practice for up to 5 PSMA-avid radiation fields. SBRT must be initiated within 90 days following initiation of apalutamide therapy. 
SBRT will be delivered in 1 to 5 fractions, and the dose and fractionation schedule will depend on the size and location of the lesion/radiation field and the surrounding normal tissue constraints in accordance with AAPM Task Group 101 recommendations. Typical doses include 16 – 24 Gy in 1 fraction, 40 – 50 Gy in 4 fractions, and 40 – 60 Gy in 5 fractions.

Safety Assessments	Patients will be assessed for adverse events (AEs) at each monthly clinic visit while on the study treatment. Adverse events will be graded according to the National Cancer Institute (NCI) Common Terminology Criteria for Adverse Events (CTCAE) Version 4.03. Type, incidence, severity, timing, seriousness, and relatedness of AEs, and laboratory abnormalities will be reported.
Efficacy Assessments	Disease assessments will be performed as scheduled according to the calendar, regardless of treatment delays resulting from toxicity. PSA measurements will be performed every 4 weeks until the time of

	PSA progression by PCWG criteria. PSMA-PET imaging will be performed at baseline and is optional at the time of PSA progression.

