4.4 DURATION OF FOLLOW UP

For safety follow up, patients will be followed for adverse events until 30 days after completion of treatment, removal from study, or until death, whichever occurs first. Patients removed from study for unacceptable treatment related adverse event(s) will be followed until resolution or stabilization of all treatment related adverse events to Grade 2 or lower.

Patients will be followed on study until confirmed PSA progression by PCWG criteria.

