7.1.7 Concomitant Medications/Therapies

All concomitant medication and concurrent therapies will be documented from screening until 30 days after the last dose of study drug. Name, indication for administration, and dates of medication or therapy will be captured.

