10 END OF TREATMENT

A patient may be discontinued from study treatment at any time if the patient or the Investigator feels that it is not in the patient's best interest to continue on study. If a patient's study treatment must be discontinued, this will not result in automatic withdrawal of the patient from the study.

Study treatment with apalutamide will be discontinued for the following reasons, whichever occurs first:

- Disease progression by PCWG criteria. PSA progression is defined as increase of at least 2 ng/mL and 25% above the nadir or baseline on study, whichever is lower, confirmed on repeat measurement at least two weeks later.
- Completion of 13 cycles of study therapy (52 weeks)
- Any episode of seizure
- Any other adverse event that cannot be adequately managed with dose modifications, including dose interruption for treatment-related adverse events that do not improve to Grade 1 or baseline within 14 days, will require study drug discontinuation
- Protocol violation requiring discontinuation of study treatment
- Patient is not compliant with study procedures
- Lost to follow-up
- Patient withdrawal of consent
- Janssen's request for early termination of study

All patients discontinuing study treatment in the absence of disease progression will enter the Post-Treatment Period for PSA monitoring until the time of confirmed PSA progression.

Follow up on study will continue at least the first occurrence of one of the following:

- Disease progression by PCWG criteria.
- Protocol violation requiring discontinuation of study treatment
- Patient is not compliant with study procedures
- Lost to follow-up
- Patient withdrawal of consent
- Janssen's request for early termination of study

If a patient is lost to follow-up, every reasonable effort must be made by the study site personnel to contact the patient and determine the reason for discontinuation/withdrawal. The measures taken to follow up must be documented. When a subject withdraws before completing the study, the reason for withdrawal is to be documented in the CRF and in the source document. Study drug assigned to the withdrawn subject may not be assigned to another subject. Subjects who withdraw will not be replaced.

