12.2 ANALYTIC PLAN

12.2.1 Analysis of Primary Endpoint

The primary endpoint for the study is the proportion of patients with undetectable serum PSA (< 0.2 ng/mL) at 6 months following completion of apalutamide therapy (18 months from date of randomization). Fisher's exact test will be used to compare the proportion in the two treatment arms. Patients who discontinue apalutamide prior to completion of 12 months of therapy for reasons other than disease progression by PCWG criteria, as well as patients who withdraw or are lost to follow up, will be considered inevaluable for this analysis. Patients who discontinue treatment for radiographic or clinical progression, even if occurring prior to receipt of SBRT in the experimental arm), would be evaluable for analysis of the primary endpoint.

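### A man who completes apalutamide and starts other anticancer therapy before month 18 probably drops out of the primary denominator, although he is a likely failure

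*Combined protocol and SAP*

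**What the plan says.** **When PSA follow-up ends.** Section 8.6 schedules PSA every 28 days after treatment until confirmed progression, then adds a second trigger: "In the event of disease progression per PCWG3 or initiation of a new non-protocol therapy, patients will be discontinued from the study". PSA is not required after that. The other passages do not carry this trigger:

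- Section 4.4: "Patients will be followed on study until confirmed PSA progression by PCWG criteria".
- Section 7.2.1 has PSA measured "every 28 days during follow up until the date of confirmed PSA progression by PCWG3 criteria".
- Under section 10, men who stop treatment without progression "will enter the Post-Treatment Period for PSA monitoring until the time of confirmed PSA progression". Its list of reasons for ending follow-up does not include new therapy.
- The abstract allows two ends only: "Patients will continue on study in follow up until disease progression by PCWG3 or withdrawal from study, whichever occurs first".

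**Who counts in the primary analysis.** Section 12.2.1 names two inevaluable groups. The first is "Patients who discontinue apalutamide prior to completion of 12 months of therapy for reasons other than disease progression by PCWG criteria". The second is introduced by "as well as patients who withdraw or are lost to follow up, will be considered inevaluable for this analysis". Men who discontinue treatment for radiographic or clinical progression are evaluable. No sentence addresses a man who completes treatment and then starts something else.

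**What is recorded.** Section 7.1.7: "All concomitant medication and concurrent therapies will be documented from screening until 30 days after the last dose of study drug". Section 6 instead wants every treatment during the trial on the case report form.

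**The concern.** Success needs a PSA below 0.2 ng/mL. PCWG PSA progression (sections 7.1.8 and 10) needs a confirmed rise of at least 2 ng/mL and 25% above the lower of nadir and baseline. Between the two, a man is failing the endpoint but has not progressed. If he starts other therapy there, between months 12 and 18, section 8.6 takes him off study and his month-18 PSA is no longer required. If section 12.2.1 then treats him as withdrawn, he leaves the denominator.

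That exclusion is informative. It follows from a decision made when arm and PSA are known, because section 5.2 says there is no blinding, and it removes men who would mostly be failures. About seven successes against one are expected, so the denominators matter when the result is close.

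**Working it through.** **1. Which reading of section 12.2.1 applies?** The man has not stopped apalutamide early and is not lost to follow-up. He did not discontinue treatment for progression either. Only the word *withdraw* can reach him.

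- For withdrawal: the abstract ends follow-up only at progression or withdrawal from study, and he has not progressed. Section 10 pairs discontinuation with withdrawal as one term when it describes documenting the reason. Section 11 lets the Sponsor-Investigator decide that a patient is withdrawn.
- Against: section 10 lists withdrawal of consent as its own reason and does not list new therapy. But that list governs when follow-up ends, not who is evaluable, and no passage counts a missing PSA as a failure.

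The first reading is better supported, so he is probably inevaluable. The text does not say so outright.

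**2. The plan's own power.** Inputs from section 12.2.5: 30 per arm, 10% inevaluable, 25% vs 2.5%, one-sided alpha 0.10, Fisher's exact test. Evaluable per arm: 30 × 0.9 = 27. Expected successes: 27 × 0.25 = 6.75 and 27 × 0.025 = 0.675.

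For x of n₁ (SBRT) and y of n₂ (control), with m = x + y:

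p = Σ over k ≥ x of C(n₁,k)·C(n₂,m−k) / C(n₁+n₂,m)

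Summing the two binomial probabilities over all tables with p ≤ 0.10 gives power of **83.6%**, which matches the stated 84%.

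**3. What can one exclusion do?**

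- 5/27 vs 1/27: [C(27,5)·27 + C(27,6)] / C(54,6) = (2,179,710 + 296,010) / 25,827,165 = **0.096**.
- Exclude one control failure, 5/27 vs 1/26: [C(27,5)·26 + C(27,6)] / C(53,6) = (2,098,980 + 296,010) / 22,957,480 = **0.104**.

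So one man can move a borderline result across 0.10. Exclusions in the other arm push the opposite way: 6/27 vs 2/27 gives 0.125, and dropping three SBRT-arm failures (6/24 vs 2/27) gives 0.090.

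**4. How robust are results nearer the planned effect?** Same formula, excluding control failures only:

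| Result | p | Exclusions survived | p after |
|---|---|---|---|
| 7/27 vs 1/27 | 0.025 | 10 (7/27 vs 1/17) | 0.098 |
| 6/27 vs 1/27 | 0.050 | 6 (6/27 vs 1/21) | 0.097 |
| 4/27 vs 0/27 | 0.056 | 7 (4/27 vs 0/20) | 0.098 |

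At 7/27 vs 1/27, close to the planned rates, ten excluded control failures do not overturn the result.

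**5. Power if such men count as non-successes.** If a fraction f of would-be successes in both arms starts other therapy first, the rates become 0.25(1 − f) and 0.025(1 − f), still with 27 per arm. Both values of f are assumptions:

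- f = 5% (23.75% vs 2.375%): power **81.1%**.
- f = 10% (22.5% vs 2.25%): power **78.1%**.

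**6. Is the start date captured?** Section 7.1.7 stops 30 days after the last dose: 364 + 30 = 394 days, about month 13. The window of interest runs to month 18. Section 6 has no such cut-off, so the two passages disagree.

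**The case against.** The best defence is that the plan already handles this man. He is a withdrawal, hence inevaluable, and falls within the 10% allowance, so only a clarifying sentence is missing. The reading is probably right, but it does not remove the problem. The allowance covers lost sample size, not the selective loss of likely failures.

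The group is also narrow. It takes a completer with PSA at or above 0.2 ng/mL, no PCWG progression and new therapy within six months, while the study design places physician-choice therapy at PSA progression. Some of these men may have radiographic or clinical progression and so fall under a progression rule. This stands and limits the size of the point.

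Recording is partly covered as well: section 10 requires the reason for withdrawal on the case report form, and a site applying section 8.6 must know that therapy has started. Only an explicit start date after day 30 is unclear.

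Finally, counting new therapy as non-success is one choice of estimand, and continuing PSA to month 18 regardless is another. That is fair. The first can be applied without a PSA that section 8.6 no longer requires.

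**Conclusion.** The concern holds at low to moderate severity. The stopping rule in section 8.6 and the exclusion rule in section 12.2.1, on the better-supported reading, together remove likely failures from the primary denominator by a post-randomization decision in an open-label trial.

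A reader might infer more than the documents support:

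- *That the result is biased toward SBRT, or toward control.* The documents give no rate of new therapy and no arm difference. The direction is unknown.
- *That the sample size is wrong.* The stated 84% reproduces at 83.6%.
- *That the primary conclusion is fragile in general.* The p-value changes shown come from chosen borderline tables. Results near the planned effect withstand many exclusions.
- *That power falls sharply.* That needs large and unequal losses, which fit poorly with a group that is probably small.

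The verdict rests on reading discontinuation under section 8.6 as withdrawal, on 27 evaluable men per arm, and on the assumption that most men who start other therapy with PSA at or above 0.2 ng/mL would not have met the endpoint at month 18.

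**What to change.** 1. **Section 12.2.1:** state that a man who completes apalutamide and starts non-protocol anticancer therapy before the month-18 PSA stays in the denominator as a non-success. Add a sensitivity analysis using the observed month-18 PSA where one was obtained. It may hold few values, since section 8.6 does not require that PSA.
2. **Follow-up passages:** reconcile section 8.6 with 4.4, 7.2.1, 10 and the abstract on when PSA collection ends, and say whether discontinuation under 8.6 is a withdrawal for section 12.2.1.
3. **Recording:** reconcile section 7.1.7 with section 6 so that the start date of such therapy is recorded through month 18.

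The cost is protocol wording and one date field at PSA contacts that already take place. Success becomes slightly harder to reach. The 83.6% power holds only if 25% and 2.5% are the rates under the stricter definition; step 5 of the working gives the loss otherwise. The rule should be fixed before the primary analysis.

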8.7 AT CONFIRMED PSA PROGRESSION (+ 28 day window)

- PSMA PET scan (optional)

- All patients can be treated at their physician's discretion as standard of care, after coming off study treatment.
- Perform and record ECOG performance status

9 ADVERSE EVENT REPORTING REQUIREMENTS

9.1 DEFINITIONS

9.1.1 Adverse Events (AE)

An AE is any untoward medical occurrence in a clinical study patient administered a medicinal (investigational or non-investigational) product. An AE does not necessarily have a causal relationship with the treatment. An adverse event can therefore be any unfavorable and unintended sign (including an abnormal finding), symptom, or disease temporally associated with the use of a medicinal (investigational or non-investigational) product, whether or not related to that medicinal (investigational or non-investigational) product. (Definition per International Conference on Harmonisation [ICH]).

This includes any occurrence that is new in onset or aggravated in severity or frequency from the baseline condition, or abnormal results of diagnostic procedures, including laboratory test abnormalities.

Examples of AEs include but are not limited to:

- Clinically significant abnormal laboratory findings (see below)
- Clinically significant signs and symptoms
- Changes in physical examination findings
- Worsening of signs and symptoms of the malignancy under study. *Disease progression assessed by measurement of malignant lesions on radiographs or other methods should not be reported as an adverse event, unless the outcome is fatal during the study or within the safety reporting period – see definition of serious adverse event below.*
- Signs or symptoms resulting from dose overdose, dependency, withdrawal, abuse, and/or misuse
- Drug interactions
- Exposure in utero (pregnancy)

For laboratory abnormalities, the criteria for determining whether an abnormal test finding should be reported as an adverse event are as follows:

- Test result is associated with accompanying symptoms, and/or
- Test result requires additional diagnostic testing or medical/surgical intervention, and/or
- Test result leads to a change in study dosing outside of protocol-stipulated dose adjustments or discontinuation from the study, significant additional concomitant drug treatment, or other therapy, and/or Test result is considered to be an adverse event by the Investigator

9.1.2 Adverse Events of Special Interest

Adverse events of special interest are events that Janssen Scientific Affairs is actively monitoring as a result of a previously identified signal (even if non-serious).

There are no adverse events of special interest identified for apalutamide.

